2. STUDY OBJECTIVES

2.1. Primary Objective

The primary objectives of this study are to assess:

- The long-term safety of CCH in the treatment of EFP commonly known as cellulite in adult women
- The safety of CCH when used for retreatment in the treatment of EFP commonly known as cellulite in adult women
- The long-term immunogenicity profile of CCH following treatment of EFP commonly known as cellulite in adult women

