3.1.2. Category II

Subjects should have not received any collagenase treatments since the completion of double-blind study.

Subjects who showed an improvement in cellulite severity of at least two levels in at least one buttock in both the PR-PCSS and the CR-PCSS (ie, 2-level composite responder) in the double-blind study.

These subjects will be observed for time to reduction of response (defined in section 4.4.1) and safety approximately every 6 months for 2 years and will be observed annually for up to 3 years (Day 1080) from Day 71 of the double-blind study.

- Category II subjects must have at least 1-level composite response reduction (ie, reduction of response by at least 1-level in the PR-PCSS and CR-PCSS ratings) compared to Day 71 of the double-blind study (EN3835-302/303) AND no longer maintain 2-level composite response compared to baseline in the EN3835-302/303 study on either or both buttocks to be eligible for a retreatment course. If there is a composite worsening of cellulite severity, the confirmation of loss of response will be established during a follow-up visit ~2 weeks after the loss of response is detected at Day 180, if the loss of response is not confirmed then the subject will not be eligible for retreatment in this study.

One and only one retreatment course in up to 2 qualifying buttocks concurrently will be offered to eligible Category I and Category II subjects during this 3-year study. The subjects in Category I and/or eligible Category II subjects will receive a retreatment course consisting of 3 treatment sessions separated by 21 days (Day 1, 22, and 43). Each treatment session will consist of 12 injections (0.07 mg/0.3 mL per injection) of CCH for a dose of 0.84 mg and volume of 3.6 mL (identical to the treatment course administered in the double-blind study), in each qualifying buttock (see

Table 5) in up to two buttocks treated concurrently.

After initiation of retreatment, the safety and cellulite severity will be assessed on Days 22, 43, and 71. The Category I and Category II subjects who received retreatment will have safety assessment completed during the observational visits at Months 12, 18, 24, and 36 from Day 71 of the double-blind study.

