The Category II subjects that have not shown at least 1-level composite reduction AND/OR have a buttock that has maintained at least a 2-level composite response (ie, have maintained a successful response), and/or Category I and/or Category II subjects who are eligible for a retreatment course but opted not to receive retreatment will have cellulite assessments at Months 12, 18, 24, and 36 from Day 71 of the double-blind study. If the subject's buttock(s) become eligible for retreatment based on the ratings during an observational visit and if they have not already received a course of retreatment in this study, then they will be offered one course of retreatment for the eligible buttock(s); one course of concurrent treatment for up to two eligible buttocks.

If a treatment period overlaps a scheduled observational visit, the observational visit will be skipped, and the subject will re-enter the observational schedule at the next interval visit. For example, if a subject initiated retreatment on Day 351 (which would then be Treatment Visit 1), the treatment period would proceed for approximately 71 days until Day 421 (Treatment Visit 4) and the Observational Visit at Day 360 would be skipped; the subject's next observational visit would be Day 540.

[figure not shown]

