Prior/concomitant medications/procedures ^c	X	X	X	X	
Anti-AUX-I/anti-AUX-II antibody level	X	X	X	X	
Subject Cellulite Assessments					
• Review assessments’ training and use materials	X	X	X	X	X
• Patient Reported Photonumeric Cellulite Severity Scale (PR-PCSS) ^{d,e}	X	X	X	X	X
• Subject Global Aesthetic Improvement Scale (S-GAIS) ^d	X	X	X	X	
• Patient Reported Cellulite Impact Scale (PR-CIS) ^d	X	X	X	X	
• Subject Satisfaction With Cellulite Treatment Assessment ^d	X	X	X	X	
• Subject Self-Rating Scale (SSRS)	X	X	X	X	
Investigator Cellulite Assessments					
• Review assessment’s training and use materials	X	X	X	X	X
• Clinician Reported Photonumeric Cellulite Severity Scale (CR-PCSS) ^e	X	X	X	X	X
Local safety assessments ^f	X	X	X	X	X
Adverse events	Monitored throughout study				

FOOTNOTES:

- ^a Unscheduled visits may be done as deemed necessary at any time during the study to ensure subject safety; assessments done at unscheduled visits are at the discretion of the investigator. No photographs or cellulite severity assessments will be done at unscheduled visits.
- ^b If the composite (CR-PCSS and PR-PCSS) ratings worsen by at least 1-level composite response ratings for a subject, an additional visit should be scheduled 14 days (± 5 days) later to confirm reduction of response, via re-assessment with the CR-PCSS and PR-PCSS. If reduction of response is confirmed, subjects will be offered one course of retreatment (one and only one course of retreatment in up to 2 buttocks concurrently will be offered to an individual subject during this open-label study from Visit 1 to Visit 5 (approximately 6 to 36 months after Day 71 of the double-blind study, respectively). The Sponsor has

Table 3: Schedule of Events: Category I/II Subjects – Observation Assessments (Continued)

decided to terminate the EN3835-304 clinical trial at the completion of 3-year time point (Day 1080) and will offer voucher(s) for commercially approved Qwo redeemable only for those trial participant(s) who will miss their potential retreatment opportunity due to this decision. Retreatment will only be offered following confirmation of eligibility through cellulite assessments performed at the Day 1080 visit for those participants, and a confirmation visit (as applicable).

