4.5.1.2. Adverse Events during Open-label Period

Adverse Event Categorization Before Retreatment

The AEs will be associated with time periods in the open label study period based on the start date of the AE compared to time period start date, as below:

- Start of Open-label Period – <Day 360 (M12)
- ≥Day 360 (M12) – <Day 540 (M18)
- ≥Day 540 (M18) – <Day 720 (M24)
- ≥Day 720 (M24) – <Day 1080 (M36)

Adverse Event Categorization after Retreatment

An AE will be associated with a treatment session during the retreatment session based on the start date of the AE compared to the date of the injections.

- AEs (which occur or worsen) with a start date between the Day 1 visit date and the day prior to the next dose or, if no further dose, the Day 71 visit date, will be associated with Treatment Session 1.
- If study drug is administered at the Day 22 visit, AEs (which occur or worsen) with a start date between the Day 22 visit date and the day prior to the next dose or, if no further dose, the Day 71 visit date, will be associated with Treatment Session 2.
- If study drug is administered at the Day 43 visit, AEs (which occur or worsen) with a start date between the Day 43 visit date and the Day 71 visit date will be associated with Treatment Session 3.
- AEs with a start date on or after Day 71 of retreatment will be aligned with observational assessment visits as, AE occurring in time period:
 - ≥Day 71 of retreatment – <Day 360 (M12)
 - ≥Day 360 (M12) – <Day 540 (M18)
 - ≥Day 540 (M18) – <Day 720 (M24)
 - ≥Day 720 (M24) – <Day 1080 (M36)

Refer to section [6.3.1.1](#) to identify AE time period status when the start date of an AE is unknown.

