AEs Before Retreatment: The new AEs recorded on or after Open-label Period starts but before retreatment in the open-label study will be summarized for subjects in Open-label Observation Population. This will include AEs of all Category I and II subjects recorded before retreatment and AEs of all Category III subjects.

An overall summary of new AE will be presented by subject category (ie, Category I, II, III, and Overall) and by time period as described in section 4.5.1.2, and will include:

- Any new AE
- Any new AE of special interest
- Any new serious AE

- Any new mild, moderate, and severe AE
- Any new AEs leading to study discontinuation
- Any new AEs resulting in death

The following summary tables will be presented by SOC and PT by subject category (ie, Category I, II, III, and Overall):

- All AEs
- AEs by Severity
- Serious AEs
- AEs leading to study discontinuation
- AEs resulting in death
- AEs of Special Interest

Serious and most common non-serious AE by order of frequency (Most frequent, 2nd most frequent and 3rd most frequent) will be summarized by PT. Most common non-serious AEs are any preferred term that at least 5% of the subjects reported at least once.

Subject listings of all AEs, serious AEs, AEs leading to study discontinuation, AEs resulting in death and AEs of Special Interest will be provided.

AEs During and after Retreatment: The new AEs recorded on or after retreatment in the open label study will be summarized for subjects in OLR Population. This will include AEs of all Category I and II subjects recorded after retreatment.

An overall summary of new AE and new AE related to study drug recorded after retreatment will be presented for each subject category (ie, Category I, II and Overall) by treatment sessions and time period (ie, all study periods and each study period as described in section 4.5.1.2), and will include:

- Any new AE
- Any new AE of special interest
- Any new serious AE
- Any new mild, moderate, and severe AE
- Any new AEs leading to study drug withdrawn/interruption
- Any new AEs leading to study discontinuation
- Any new AEs resulting in death

The following summary tables will be presented by SOC and PT by subject category (ie, Category I, II, and overall) and each treatment sessions [TX1, TX2, TX3, and Total ('Total' includes AEs reported during Treatment Session 1, 2, and 3, and Observation Period post Day 71 of retreatment)]:

- All AEs
- AEs by causal relationship to study drug
- AEs by Severity

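### AEs from Day 71 of retreatment onward are grouped on the double-blind clock, so no planned summary shows late events by time since retreatment

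*SAP*

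**What the plan says.** Retreatment safety is one of the primary objectives in SAP section 2.1: "The safety of CCH when used for retreatment in the treatment of EFP commonly known as cellulite in adult women".

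For AEs after retreatment, section 4.5.1.2 uses two clocks. From retreatment Day 1 up to Day 71, an AE is assigned to Treatment Session 1, 2 or 3 by its start date relative to the injections. After that the rule changes: "AEs with a start date on or after Day 71 of retreatment will be aligned with observational assessment visits". The resulting periods run from Day 71 of retreatment to before Day 360, then to before Day 540, Day 720 and Day 1080. Section 3.1.2 fixes the origin of those days by describing "observational visits at Months 12, 18, 24, and 36 from Day 71 of the double-blind study".

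The start of retreatment is not fixed on that clock. Table 3, footnote b, says that the single course is offered "during this open-label study from Visit 1 to Visit 5 (approximately 6 to 36 months after Day 71 of the double-blind study, respectively". Section 3.1.2 gives the example of a course begun on Day 351, for which "the treatment period would proceed for approximately 71 days until Day 421".

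On reporting, section 7.7.2 states: "The new AEs recorded on or after retreatment in the open label study will be summarized for subjects in OLR Population". The OLR Population (Table 16) is everyone in the TRR population who is retreated at any time in the open-label period. The periods of section 4.5.1.2 are used in the overall AE summary. The SOC/PT tables are split by session (TX1, TX2, TX3) and a total that also pools all observation after retreatment Day 71.

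**The concern.** A summary of late AEs after retreatment should show how long after exposure they occur. A period counted from the double-blind study does this only if all subjects are retreated at about the same study day, and the design allows starts spread over many months. A column headed Month 24 to Month 36 can then combine one subject in her third month after retreatment with another well into her third year. A cluster of events at a given interval after retreatment would be spread over several columns.

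A second question is the denominator. A subject retreated late in the study belongs to the OLR Population but has no post-retreatment time in the early periods. If she is counted there, the early percentages are too low. Both matters bear on a primary objective.

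**Working it through.** **Inputs.** Period limits (Day 360, 540, 720, 1080): section 4.5.1.2. Origin of the study day: double-blind Day 71, section 3.1.2. Retreatment day: AE start date minus date of first injection plus 1, which is the AE Onset Day (retreatment phase) in Table 17. The SAP gives no distribution of retreatment dates, so the start days below are illustrative. The earliest is Day 181, just after the Day 180 visit. The latest is 720 + 30 (visit window) + 14 + 5 (confirmation visit and its window) + 14 (Screening B) = Day 783. That is not a hard limit, because Table 2, footnote b, allows a later repeat of Screening B.

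**The plan's own figure.** With start day s, retreatment Day 71 falls on study day s + 70. For s = 351 this is 351 + 70 = 421, which agrees with section 3.1.2.

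**Retreatment days held by each period.** A period from study day a to b contributes retreatment days max(a, s + 70) - s + 1 to b - s + 1, provided s + 70 ≤ b. For s = 181 in the last period: 720 - 181 + 1 = 540 and 1079 - 181 + 1 = 899. For s = 735: retreatment Day 71 is study day 805, so the range is 71 to 1079 - 735 + 1 = 345.

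| Start day | Before Day 360 | Day 360-539 | Day 540-719 | Day 720-1079 |
|---|---|---|---|---|
| 181 | 71-179 | 180-359 | 360-539 | 540-899 |
| 351 | none | 71-189 | 190-369 | 370-729 |
| 555 | none | none | 71-165 | 166-525 |
| 735 | none | none | none | 71-345 |
| 783 | none | none | none | 71-297 |
| All starts 181-783 | 71-179 | 71-359 | 71-539 | 71-899 |

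In the last period, the Day 181 and Day 735 starts do not overlap at all (540-899 against 71-345). The SAP's own Day 351 subject has no time in the first period, since her retreatment Day 71 comes after that period ends.

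**Starts with no time in a period.** The last start that contributes is b - 70: 359 - 70 = 289, 539 - 70 = 469 and 719 - 70 = 649. Starts on or after Day 290, Day 470 and Day 650 therefore contribute nothing to the first, second and third periods respectively.

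**Denominator.** Section 6.1 offers two general rules: the number of subjects in the population, or, where the denominator changes over time, those with non-missing values at the visit. The second has no clear meaning for AEs, which are not measured at visits. Section 7.6.3 restricts reduction of response after retreatment to subjects already retreated by that visit. Section 7.7.2 has no such rule for AEs. If every OLR subject were counted and a share f were past retreatment Day 71 before Month 12, a 10% incidence among those at risk would show as 10% × f:

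| f (assumed) | 30% | 50% | 70% | 90% |
|---|---|---|---|---|
| Shown incidence | 3% | 5% | 7% | 9% |

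**The case against.** Several points on the other side stand.

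- AEs during the retreatment course are anchored on injections. Only AEs from retreatment Day 71 onward are affected, and the calendar periods are named only for the overall summary.
- A reader might infer that the periods count events in subjects not yet retreated. They do not: section 7.7.2 tabulates AEs before retreatment separately, in the Open-label Observation Population. Such subjects could enter only through the denominator.
- A reader might also take the dilution as established. The SAP does not say that all OLR subjects are the denominator for each period. It leaves the rule open, and the table shells in SAP Module 2, which are not part of this document, may settle it. The share f is unknown. Category I subjects need no loss of response to qualify, so early retreatment may dominate and the dilution may be slight.
- Not every period mixes weeks with years. The first two cannot extend past retreatment days 179 and 359 under these starts; only the last two go beyond one year.
- It would be too strong to say that the tables cannot separate events after retreatment from those before. They do, drug-related AEs are tabulated, and all AEs are listed.

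It can also be said that visit-aligned periods match the pre-retreatment ones and suit a descriptive study. That supports keeping them as one display. It does not supply the missing one, because the SOC/PT tables pool everything after retreatment Day 71 into a total, and the retreatment onset day in Table 17 is not used in any summary named in section 7.7.2.

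**Conclusion.** The point holds for AEs starting on or after Day 71 of retreatment. Their periods carry no fixed time since exposure, and no planned summary shows them by time since retreatment. For starts of Day 181 to 783 the last period spans retreatment days 71 to 899, and starts from Day 290 onward are absent from the first. These limits follow from date arithmetic; how strongly the mixing affects the tables depends on the actual retreatment dates, which the SAP does not give.

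The denominator part is an unfixed rule, not a stated error. The 3% to 9% range depends on two assumptions: that all OLR subjects would be used, and that f lies between 30% and 90%. The document does not support a claim that post-retreatment AEs in general are misassigned, or that unexposed subjects add events.

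**What to change.** In sections 4.5.1.2 and 7.7.2, summarize AEs from retreatment Day 71 onward by days since first retreatment injection, using the AE Onset Day (retreatment phase) from Table 17. Periods could be, for example, Day 71 to <180, 180 to <360, and 360 or later. Take as denominator the OLR subjects still followed at the start of each period, and add exposure-adjusted rates. Both are needed even with these periods: followed to study day 1079, only subjects who start by Day 720 reach retreatment Day 360 (1079 - 720 + 1 = 360).

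The calendar periods may stay as a secondary display. If they do, state that each percentage counts only subjects with post-retreatment time in that period, in line with section 7.6.3.

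The cost is one derived period variable and one added table set. No new data are needed, and study conduct does not change.

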4.5.1.3. Intensity of Adverse Events

Intensity (or severity) of AEs will be graded as “Mild”, “Moderate” or “Severe”. For AEs with missing severity, the most severe assessment will be imputed for analyses, following worst case principle. If the intensity of an AE changes, then the most severe intensity during the continuous episode will be recorded.

4.5.1.4. Relationship to Study Drug

Causal relationship of AE with study drug will be classified by the Investigator and will be reported as follows:

- Not related

- Unlikely related
- Possibly related
- Probably related

Related adverse events are AEs with the relationship described by the investigators as “probably related” or “possibly related”. “Not related” or “Unlikely related” causality assessments are considered as negative causality.

The ongoing AE’s from EN3835 302/303 studies at the time screening will be imported in the open label study and their relationship with study drug in EN3835 302/303 will also be classified as above.

Any missing relationship of an AE to study drug will be considered as related to study drug for the analyses, following worst case principle.

4.5.2. Potentially Clinically Important Laboratory Values

Potentially clinically important (PCI) laboratory values are presented in Table 14 below:

Table 14: Potentially Clinically Important Laboratory Criteria

Parameter	PCI Low: Less than or equal to	PCI High: Greater than or equal to
Hemoglobin (g/L)	100	190
Hematocrit (%)	30	60
Platelets (10 ⁹ /L)	100	650
ALT (U/L)		3×ULN
AST (U/L)		3×ULN
Creatinine (μmol/L)		300
BUN (mmol/L)		12

ALT=Alanine transaminase; AST=Aspartate transaminase; BUN=Blood urea nitrogen; ULN=Upper limit of normal

4.5.3. Potentially Clinically Important Vital Sign Values

Vital sign values are PCI if they meet both the observed value criteria and the change from baseline criteria. The PCI vital sign values are presented in Table 15 below:

Table 15: Potentially Clinically Important Vital Sign Criteria

Parameter	PCI Low	PCI High
Systolic blood pressure	≤90 mmHg and decrease ≥20 mmHg from baseline	≥180 mmHg and increase ≥20 mm Hg from baseline
Diastolic blood pressure	≤50 mmHg and decrease ≥15 mmHg from baseline	≥105 mmHg and increase ≥15 mmHg from baseline
Pulse rate	≤50 bpm and decrease ≥15 bpm from baseline	≥120 bpm and increase ≥15 bpm from baseline
Respiratory rate	≤8 brpm and decrease ≥7 brpm from baseline	≥25 brpm and increase ≥7 brpm from baseline
Temperature		≥38.3°C and increase ≥1.1°C from baseline

bpm=Beats per minute; brpm=Breaths per minute

4.5.4. Immunogenicity

Seropositivity and titer levels for both anti-AUX-I and anti-AUX-II antibodies will be obtained from each analyzed sample. Samples with a positive titer value will undergo a log transformation for analyses. Samples with titer level less than 1 will be assigned or imputed as a log transformed titer of zero (0) for analyses.

All samples with seropositive antibodies will be tested for neutralizing antibodies. Samples will be classified as positive or negative for neutralizing antibodies based on the results of these analyses.

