3.11.6. Immunogenicity Samples

Immunogenicity variables include anti-AUX-I/anti-AUX-II binding (ie, anti-drug) and neutralizing antibody results. Serum samples will be collected at Screening (Day 71 of double-blind study), Treatment visits (Day 22, 43, and 71), and Observation Visits (Day 360, 540, 720, and 1080/EOS) for all subjects for the determination of serum anti-AUX-I and anti-AUX-II antibody levels.

For Category I subjects and/or eligible Category II subjects receiving retreatment, a subset (based on every other sample from the Treatment Visit 4 upper and lower quartiles of binding antibody titers) of subject samples will be tested for neutralizing antibodies from these visits.

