5. ANALYSIS POPULATIONS

The study will use following analyses population for data summarization.

Table 16: Analysis Population

Population	Definition	Displays
Day-180 Observational Population	The Day-180 Observational Population includes all rollover subjects from studies EN3835-302/303.	The protocol deviations, demographic characteristics and safety analysis for the data obtained from Screening to Day 180 will be based on this population. The reduction of response, complete loss of response, and all cellulite assessments (ie, changes in CR-/PR-PCSS, PR-CIS, S-GAIS, SSRS, and subject satisfaction with cellulite treatment at Day 180 will be summarized.
Prior to Day 180 Population	Prior to Day 180 Population includes all subjects who did not meet inclusion criteria #2 or inclusion criteria #5 or those who withdrew from the study due to SAE/AE, or lost to follow-up prior to Day 180.	The protocol deviations, demographic characteristics and safety analysis for the data obtained from Screening to Day 180 will be based on this population.
Open Label Observation Population	The Open Label Observation Population includes all subjects who enter the open-label study and received active CCH in EN3835-302 or EN3835-303. This population will include all Category I, II, and III subjects including the subjects who received retreatment in the Open-label Period.	The protocol deviations, demographic characteristics and safety parameters for the open label period prior to retreatment will be summarized based on this population.
Time to Reduction of Response (TRR) Population Before Retreatment	The TRR Population Before Retreatment includes all subjects who have at least a 1-level or 2-level improvement in both CR-PCSS and PR-PCSS ratings during the double-blind study for either/both treated buttocks. This population will include Category I and II subjects. Reduction of response will be evaluated separately for subjects who have at least a 1-level and 2-level improvement in both CR-PCSS and PR-PCSS ratings during the double-blind study in each treated buttock. The reduction of response prior to retreatment will be analyzed using this population.	The analyses of cellulite assessments prior to retreatment, and demographic characteristics will be based on this population.

Table 16: Analysis Population (Continued)

Population	Definition	Displays

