6. STATISTICAL METHODS

6.1. General Methodology

All summary tables and data listings will be prepared using version 9.4 or later of statistical analysis software (SAS®) software.

Continuous data will be summarized using descriptive statistics (number of subjects [n], mean, standard deviation [SD]/ or standard error [SE], median, minimum [min], and maximum [max]) and discrete data will be summarized using frequency counts and percentages, the denominator will be based on the number of subjects in the appropriate population. For the purpose of display, the summary results will be rounded as follows:

- Min and max: same number of decimal places as the raw data.
- Mean and median: one more decimal place than the raw data.
- SD/SE: two more decimal places than the raw data.
- Percentages will be displayed with one decimal precision. A zero count will not have the associated percentage presented on the table (ie, no 0%).
- The standard form of a percentage change variable is 0 decimal places.

For categorical variables with missing values, a category documenting the frequency of missing values will be displayed in the summary tables.

Summary tables, subject listings, graphs and any supportive SAS output will include a “footer” of explanatory notes that will indicate, when applicable:

- Date of data extraction
- Date and time of output generation
- SAS program name, including the path, that generates the output

When calculating percentages, the denominator will be based on the number of subjects with non-missing values. If the denominator is expected to change over time, then the denominator used to calculate the percentage should be based on the number of subjects with non-missing values at each visit. Any subject removed from an analysis will be noted at the bottom of the table along with the reason the subject was removed.

Null summary tables will be presented with a note stating that “No Subjects Met Criteria.” Subject listings of all data from the CRFs as well as any derived variables will be presented.

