7.7.7. Immunogenicity

The immunogenicity data for subjects who entered the Open-label Period of the study will be summarized separately before retreatment using Open-label Observation Population, and after retreatment using OLR Population.

Immunogenicity Data Before Retreatment: The immunogenicity data at Screening (Day 71 of double-blind studies) and Observation Visits prior to retreatment will be summarized by Subject Category (ie, Category I, II, III, and Overall) for subjects in Open-label Observation Population.

Immunogenicity Data After Retreatment: The immunogenicity data at Screening B (screening during retreatment phase), Treatment Visits (TX2, TX3, and TX4) and Observation Visits after retreatment through end of study will be summarized for subjects in OLR Population.

The immunogenicity data of binding and neutralizing anti-AUX-I and anti-AUX-II antibodies will be summarized using the number of subjects with an immunogenicity sample, the percentage of subjects with a positive sample, and a descriptive summary of the average titer level of the positive samples at the assessment visits. The titer levels will be logarithmically transformed prior to being summarized descriptively.

The number and percentage of assayed serum samples that will detect the presence or absence of neutralizing antibodies (positive/negative) to AUX-I and AUX-II will be summarized by antidrug antibody quartiles for the retreated subjects using frequency counts and percentages at Day 71/End of Retreatment phase.

The listings of immunogenicity data will be presented separately for the All Subjects prior to retreatment and for subjects in OLR Population after retreatment.

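### Sections 4.5.4 and 3.11.6 give conflicting rules for neutralizing-antibody testing; under the subset rule the by-visit percentage in 7.7.7 does not estimate the rate in retreated subjects

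*SAP*

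**What the plan says.** Section 4.5.4 sets a general rule: "All samples with seropositive antibodies will be tested for neutralizing antibodies". It makes no exception for retreated subjects.

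Section 3.11.6 sets a different rule for Category I and eligible Category II subjects receiving retreatment. There the testing covers "a subset (based on every other sample from the Treatment Visit 4 upper and lower quartiles of binding antibody titers) of subject samples". The sentence ends "of subject samples will be tested for neutralizing antibodies from these visits", and the visit list just before it reads "Serum samples will be collected at Screening (Day 71 of double-blind study), Treatment visits (Day 22, 43, and 71), and Observation Visits", followed by the days of those observation visits.

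Section 7.7.7 plans two kinds of neutralizing-antibody display:

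- A by-visit summary of binding and neutralizing antibodies, including "the percentage of subjects with a positive sample". It uses the Open-label Observation Population before retreatment and the OLR Population after it.
- A table by antidrug-antibody quartile for retreated subjects, at Day 71 of retreatment only.

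For percentages whose denominator changes over time, section 6.1 says that "the denominator used to calculate the percentage should be based on the number of subjects with non-missing values at each visit".

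**The concern.** For a retreated subject both rules cannot hold. One tests every seropositive sample; the other tests a sample chosen by titer that leaves out the middle of the distribution. Nothing in the SAP makes one an exception to the other. Table 18 does not mention the point, although that table lists departures from the protocol, so its silence does not show which rule is meant.

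The choice changes what the by-visit percentage means. Under 4.5.4 it describes the seropositive samples. Under 3.11.6 it describes an unweighted mix of the lowest and highest titer quartiles, and nothing in 7.7.7 restricts, weights or labels it accordingly. The long-term immunogenicity profile is a primary objective (section 2.1), and a reader could take the figure as the rate for everyone in the column.

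The subset rule may also reach samples taken before retreatment. The visits it refers to follow a list that includes Screening and the Observation Visits. Section 7.7.7 says "The immunogenicity data at Screening (Day 71 of double-blind studies) and Observation Visits prior to retreatment will be summarized by Subject Category" in the Open-label Observation Population, of which Table 16 says "This population will include all Category I, II, and III subjects including the subjects who received retreatment in the Open-label Period". On that reading, early samples of later-retreated subjects are selected on a titer measured after retreatment. They are then pooled with samples of non-retreated subjects tested under 4.5.4.

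**Working it through.** The SAP states no neutralizing rate, seropositive share or retreated share, so it has no figure of its own to reproduce. All rates and shares below are assumptions.

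**1. Fraction tested (retreated subjects with a titer)**

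| | Lowest quartile | Two middle quartiles | Highest quartile | Total |
|---|---|---|---|---|
| 3.11.6 | half of 25% | none | half of 25% | 0.5 × (25% + 25%) = 25% |
| 4.5.4 | all seropositive | all seropositive | all seropositive | all seropositive |

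**2. Bias after retreatment under the subset rule**

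Let Q1 to Q4 be the neutralizing-positive rates at a visit in the four groups formed by Treatment Visit 4 titer. Take the groups as equal in size and alternate sampling as representative within each. The denominator is non-missing values at the visit (6.1).

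- Shown = (Q1 + Q4)/2
- True = (Q1 + Q2 + Q3 + Q4)/4
- Bias = shown - true = (Q1 + Q4 - Q2 - Q3)/4

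| Assumed Q1/Q2/Q3/Q4 (%) | Shown | True | Bias (points) |
|---|---|---|---|
| 50/50/50/50 | 50 | 50 | 0 |
| 20/40/60/80 | 50 | 50 | 0 |
| 10/15/30/85 | 47.5 | 35 | +12.5 |
| 10/70/85/90 | 50 | 63.75 | -13.75 |

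If rates do not fall from Q1 to Q4, then Q2 + Q3 lies between 2×Q1 and 2×Q4. The bias then lies between -(Q4 - Q1)/4 and +(Q4 - Q1)/4. Reweighting cannot remove it, because the middle two quartiles have no chance of being tested.

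**3. Weight before retreatment, if the subset rule reaches those visits**

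Let r be the later-retreated share of the column and s the seropositive share of samples from non-retreated subjects. One quarter of later-retreated subjects are tested.

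Share of tested weight from later-retreated subjects = 0.25r / (0.25r + s(1 - r))

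| r | s = 1 | s = 0.5 |
|---|---|---|
| 10% | 0.025/0.925 = 2.7% | 0.025/0.475 = 5.3% |
| 30% | 0.075/0.775 = 9.7% | 0.075/0.425 = 17.6% |
| 50% | 0.125/0.625 = 20.0% | 0.125/0.375 = 33.3% |

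In every row later-retreated subjects count for less than their share r. These figures are weights, not biases; the effect on the percentage also depends on rates the SAP does not give.

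**The case against.** The best defence is that 4.5.4 is the general rule and 3.11.6 a specific exception for retreated subjects. The Day 71 quartile table in 7.7.7, which counts assayed samples, fits that. It is a plausible reading, though the SAP does not state it and a quartile table could equally be made under full testing. It does not rescue the by-visit percentage, because it puts the subset rule in force for the OLR Population, where that percentage goes wrong.

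The denominator may also be disputed. Section 6.1 has another sentence basing percentages on the number of subjects in the population. The visit-level rule is more specific, so it is used here, and the zero-bias cases and the bound hold only under it. If untested subjects stayed in the denominator, the figure would be 0.25 × (Q1 + Q4)/2 and could not exceed 25%. The 20/40/60/80 case would then show 12.5% against 50%. Nor does the missing-value category in 6.1 help: it counts untested subjects but does not address how the tested ones were chosen.

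The pre-retreatment extension is less certain. The visits meant in 3.11.6 could be the retreatment visits alone, so that part stays conditional.

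The limited weight of the point also stands. The summaries are descriptive, no test or decision rule uses them, and the bias may be zero. Binding-antibody results are unaffected, and the Day 71 quartile table is not at fault.

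**Conclusion.** The concern holds. The SAP contains two incompatible testing rules for retreated subjects and does not rank them. If the subset rule is in force, the pooled by-visit neutralizing-antibody percentage after retreatment does not estimate the rate in the OLR Population. Its direction of error is unknown, and the illustrative patterns run from -13.75 to +12.5 points. Whether the column before retreatment is also affected depends on which visits 3.11.6 covers. The conflict itself rests on the text alone; the sizes rest on assumed quartile rates. It should be fixed because it feeds a primary objective, but its reach is limited to descriptive neutralizing-antibody summaries.

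**What to change.** State one testing rule in both 3.11.6 and 4.5.4, and name the visits it covers.

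- **If all seropositive samples are tested:** delete the subset text in 3.11.6, and state in 7.7.7 whether binding-negative subjects count as neutralizing-negative.
- **If the subset rule applies:** report neutralizing results for retreated subjects only within the upper and lower quartiles, with the number assayed as denominator, as the Day 71 table already does. State whether the quartiles are formed on the anti-AUX-I or the anti-AUX-II titer. Drop the pooled by-visit percentage, or label it in 7.7.7 as tested-subset data. Do this in every population that includes retreated subjects: OLR and, if earlier visits are covered, Open-label Observation.

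The cost is wording in two sections and one changed display. No new assays are needed if the subset rule is in force. If the all-seropositive rule governs and only the subset was assayed, the remaining samples would have to be tested. The downside of the subset rule is that no overall neutralizing-antibody rate can be claimed for retreated subjects.
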